9.2 All-cause Mortality or Cardiovascular Hospitalization

Endpoint definition: Time from randomization to the first event in this composite endpoint (i.e., time from randomization to either death or the subject's first cardiovascular hospitalization).

For subjects who have not experienced either component of this endpoint (i.e., who are censored observations), time from randomization until the subject's last follow-up contact will be used in the analysis.

The cause of hospitalization will be based on the *site-reported* data in the CABANA electronic data capture (EDC) system. For this endpoint, cardiovascular hospitalization will not include a hospitalization to initiate therapy. For example, among patients randomized to the ablation arm, the hospitalization to perform the ablation will not be counted for this secondary endpoint. Similarly, if a patient randomized to the drug arm is hospitalized to monitor the patient while loading the initial drug therapy, that hospitalization will not be counted. All other hospitalizations designated by the clinical site as *cardiovascular* will be counted, including the hospitalization of a patient randomized to the drug arm who is hospitalized for a therapy change (either a change to a different drug therapy or for crossing over to ablation). Hospitalization to perform second or subsequent ablation procedures will be counted as a CV hospitalization event.

Statistical Methods: The analysis of this secondary endpoint will use the same methods as described for the primary endpoint and key secondary endpoint in sections 8 and 9.1, including statistical testing using the log-rank test, calculation of a hazard ratio and 95% confidence interval using the Cox model, and Kaplan-Meier cumulative event rate calculations. The level of significance for the assessment of this endpoint will be $\alpha=0.05$.

9.3 All-cause Mortality, Stroke, or Hospitalization for Heart Failure or an Acute Ischemic Event

Endpoint definition: Time from randomization to the first event in this composite endpoint.

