The intention-to-treat analyses in this trial will constitute the primary analyses and will serve as the standard for interpreting treatment differences in the key clinical outcomes. However, because a number of patients in the drug arm may cross over to receive ablation during the trial, and some patients randomized to ablation may not undergo the procedure, we will supplement the intent-to-treat comparisons of the primary endpoint and selected secondary endpoints with “on-treatment” comparisons. The “on-treatment” analysis will involve a comparison of patients who received ablation (even if originally assigned to the drug arm) versus those who did not. Statistically, this will be accomplished using the Cox proportional hazards model with ablation included in the analysis as a time-dependent covariate. This analysis will be repeated for the primary endpoint, all-cause mortality, all-cause mortality or cardiovascular hospitalization, all-cause mortality, stroke, or hospitalization for heart failure or acute ischemic events, cardiovascular death, cardiovascular death or disabling stroke, arrhythmic death or cardiac arrest, heart failure death, and cardiovascular hospitalization with and without adjustment for covariates listed in section 8.1. No analyses will include competing risks, and on-treatment analysis will not be conducted for multiple events analyses (section 9.9). For recurrent atrial fibrillation, we will only conduct this on-treatment analysis for the first episode of recurrent AF without competing risks in the 3 patient populations (Cabana box, non-cabana box, and pooled). Secondary analyses may consider other measures of recurrent atrial fibrillation (e.g., *symptomatic* recurrent AF, atrial fibrillation or atrial flutter or atrial tachycardia, and *symptomatic* atrial fibrillation, atrial flutter, or atrial tachycardia).

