The time-dependent ablation variable to be included in the analysis will be created using 3 different methods: For method 1, the ablation variable starts as 0 (no ablation) for all patients. For patients who received ablation, the ablation variable is set to 1 at the time of ablation. In method 2, the ablation variable starts as 1 for all patients who were randomized to ablation and actually received ablation. For all other patients, the ablation variable is started as 0 and set to 1 at the time of ablation if they received ablation during the trial. Method 3 has the ablation variable started as 1 for patients who were randomized to ablation. For all other patients (i.e., randomized to drug), the ablation variable is started as 0 and set to 1 at time of ablation.

Among the 3 methods described above, method 2 will be considered the main statistical method in handling cross-overs via a time-dependent variable in Cox model. The other 2 methods are considered as sensitivity analyses.

Differential treatment effects for the primary endpoint and major secondary endpoints of interest using on-treatment analyses will also be conducted. Subgroups of interest will include those listed in section 8.1.

Because treatment assignment is no longer random, results can be biased by an association between the likelihood of treatment change and the risk of a clinical event (i.e., factors that make a patient more likely to cross over may also make them more likely to have an event). Thus, such analyses will be cautiously interpreted. Each of the analyses described in this section will be covariate adjusted using the covariates described in section 8.1 for the primary endpoint.

11. Per-Protocol Analysis

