Using the methods described for the primary endpoint in Section 8, an analysis will also be performed to compare the primary endpoint and the key secondary clinical outcomes of the two treatment strategies among the subset of patients who fully satisfied the inclusion/exclusion criteria and received the treatment to which they were randomly allocated. This analysis will include patients randomized to the drug arm who were treated with drug therapy, and patients randomized to the ablation arm who underwent the ablation within 6 months following enrollment in the trial. The follow-up of drug-arm patients who crossed over to ablation will be censored at the time of the ablation. Patients randomized to the ablation arm who were not ablated within 6 months will be excluded from this analysis. Additional sensitivity analyses will be performed in which the window for ablation is varied to include a shorter interval (3 months) and a longer window (1 year).

The analyses outlined in Sections 10 and 11 will be strictly supplementary to the intent-to-treat analyses described earlier.

12. Multiple Comparisons

With the primary hypothesis and the various secondary endpoints that have been outlined, there is a multiplicity of analyses to be performed, which leads to an increased probability that at least one of the comparisons could be "significant" by chance. There are adjustments (e.g., based on the Bonferroni inequality) that could be used to preserve the overall type I error level. To attempt to adjust for the effects of the repeated significance testing that will occur as part of the interim monitoring (discussed below), plus adjust for the multiplicity of secondary endpoints, would require that very small significance levels be used for every comparison. The overall level of significance will be 0.049 for the assessment of the primary endpoint (see Section 13) and 0.05 for all secondary endpoints. However, to account in part for the multiplicity of comparisons involving secondary endpoints, we will be conservative in the interpretation of the analyses, taking into account the degree of significance, and looking for consistency across endpoints. The actual p-value for each comparison will be reported to aid in the overall interpretation. We have

also pre-specified the primary and secondary outcome variables to avoid over-interpretation of strictly exploratory comparisons.

13. Interim Analyses

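### In the on-treatment analysis of death or CV hospitalization, a drug-arm patient's crossover admission can be both the switch to ablated and the event, so the hazard ratio depends on date order

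*SAP*

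**What the plan says.** SAP 9.2 defines death or CV hospitalization as "time from randomization to either death or the subject's first cardiovascular hospitalization". Its counting rule differs by arm. For the ablation arm, "the hospitalization to perform the ablation will not be counted for this secondary endpoint". For the drug arm, an admission counts when the patient is "hospitalized for a therapy change (either a change to a different drug therapy or for crossing over to ablation"). The cause of admission is as reported by the site.

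SAP 9.9 takes time to first CV hospitalization as its first analysis. It gives no counting rule of its own and no exemption for crossover admissions.

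SAP 10 fits a Cox model with ablation as a time-dependent covariate and applies it to both endpoints: "This analysis will be repeated for the primary endpoint, all-cause mortality, all-cause mortality or cardiovascular hospitalization", with CV hospitalization alone later in the same list. The event definitions are not changed for this purpose. The recurrent-event route is closed: "on-treatment analysis will not be conducted for multiple events analyses (section 9.9"). In method 2, the main method, anyone not both randomized to ablation and ablated is coded as follows: "the ablation variable is started as 0 and set to 1 at the time of ablation if they received ablation during the trial". Methods 1 and 3 code drug-arm crossovers in the same way. Protocol 8.2.5 states the purpose: a crossover's time is credited to drug until crossover and to ablation afterwards.

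**The concern.** The on-treatment analysis exists to move crossovers' later follow-up into the ablation group. On a first-event endpoint that counts the crossover admission, this cannot happen for a patient whose crossover admission is the first counted event. Follow-up ends at the admission that delivers the ablation.

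The group charged with that event is then decided by dates. If the patient is admitted the day before, the covariate is still 0 and the event goes to not ablated. If admission and ablation share a date, the event can go to ablated with no exposure time behind it, depending on how the program orders the two. The SAP gives no same-day rule. SAP 7.3 adds a further route: an event with a missing date is placed at the nominal visit time, which can fall after the ablation.

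At stake is whether these supplementary hazard ratios can be read at all. With no true effect, the same data can give an HR on either side of 1.

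**Working it through.** **Which crossovers are affected.**
- Ablated in a counted CV admission, none earlier: switch and event coincide, and no ablated time is contributed. Affected.
- Earlier counted CV admission: follow-up has already ended, so date order is irrelevant.
- Ablated without a CV admission: switches and contributes ablated time as intended.

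The composite in SAP 9.3 counts only heart failure and acute ischemic admissions, so a crossover admission as such is not an event there.

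**Inputs.** From the documents: 2,204 patients randomized 1:1 (1,102 per arm), minimum follow-up slightly under 2 years and median about 4 (SAP introduction); crossover possibly up to 25–30% (Protocol 8.1). The plan gives no figure for this analysis, so there is none to reproduce. Assumed: follow-up *f* uniform on 2–6 years; event hazard *h* of 0.08, 0.25 or 0.40 per year; crossover proportion *p* reached by year 5; crossover unrelated to risk; all of the ablation arm ablated; all crossovers admitted; no true effect.

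**Formulas.** The crossover hazard is λ = −ln(1 − p)/5, giving 0.0211, 0.0575 and 0.0713 for 10%, 25% and 30%.

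- Event charged to not ablated: unablated patients have events at rate h + λ and ablated patients at rate h, so HR = h/(h + λ).
- Event charged to ablated: procedural admissions are added to the ablated events without adding time, so HR ≈ 1 + (λ/h)(D/A). Here A and D are the mean event-free years per ablation-arm and drug-arm patient: the averages over f of (1 − e^(−hf))/h and (1 − e^(−(h+λ)f))/(h + λ).

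Example, h = 0.08 and p = 30%: 0.08/0.1513 = 0.53. With A = 3.384 and D = 2.945, 1 + 0.891 × 0.870 = 1.78.

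| Crossover | h per year | HR, charged to not ablated | HR, charged to ablated |
|---|---|---|---|
| 10% | 0.08 | 0.79 | 1.25 |
| 10% | 0.25 | 0.92 | 1.08 |
| 10% | 0.40 | 0.95 | 1.05 |
| 25% | 0.08 | 0.58 | 1.64 |
| 25% | 0.25 | 0.81 | 1.21 |
| 25% | 0.40 | 0.87 | 1.13 |
| 30% | 0.08 | 0.53 | 1.78 |
| 30% | 0.25 | 0.78 | 1.25 |
| 30% | 0.40 | 0.85 | 1.16 |

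**Simulation check.** A Cox partial likelihood with the time-dependent covariate, 200 trials per setting, agrees with every cell to within 0.02. Across all simulations run, the 10% range was slightly wider, about 1.04–1.27 or 0.77–0.96.
- Nominal 5% rejections at 25–30% crossover: 94–100% for h of 0.08–0.25, and 77–94% for h = 0.40.
- Rejections at 10% crossover: about 80% at h = 0.08, and 17–34% at h of 0.25–0.40.
- With half the crossovers admitted, at 25–30% and h of 0.08–0.25, the HR is 0.69–0.90 or 1.10–1.35.
- The crossover admission is the first event in about 85%, 63% and 51% of crossovers at h of 0.08, 0.25 and 0.40.

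**After the fix.** With the procedural admission not counted, the HR is 0.99–1.01.

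**With a true effect.** A separate simulation set the true HR at 0.75, with hazards of 0.10–0.30, 25–30% crossover by year 4, 5% of the ablation arm never ablated and all crossovers admitted. As written, the HR was 0.41–0.61 or 0.95–1.51. With the fix it was 0.74–0.76.

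**The case against.** The strongest reply concerns weight and size. SAP 11 makes these analyses strictly supplementary, SAP 10 asks for cautious interpretation, and only two of ten listed endpoints are involved. That stands and limits the importance. The caution in SAP 10, however, is about patients who cross over having different risk. The overlap arises even when crossover is unrelated to risk, and covariate adjustment does not remove it.

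The size is also conditional. The 25–30% is an upper projection; the pilot saw 9.7% crossover at one year. The documents give neither a CV-hospitalization rate for this population nor the share of crossover ablations that sites report as CV admissions. The AFFIRM rehospitalization figures in Protocol 1.2.4 (73.0% and 80.1%, hospitalization not limited to CV causes) correspond to 0.26–0.32 per year if read as five-year risks. If crossover is three times likelier after a first CV admission (an assumption; 28% crossover, all admitted), the HR falls to 1.14 or 0.87 at h = 0.25, and 1.08 or 0.93 at 0.40. All of this stands.

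Some of the distortion belongs to the SAP 9.2 rule itself. In the separate simulation with no true effect, day-before dating gave an on-treatment HR (0.55–0.82) close to the ITT one (0.53–0.81). That counting rule is a deliberate choice for ITT and is not disputed here. Carried into SAP 10, it defeats the purpose of the time-dependent covariate.

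Three stronger readings are tempting but unsupported:
- That crossovers as a group add no ablated time. Those ablated without a CV admission do.
- That the per-protocol analysis in SAP 11 has the same fault, since "The follow-up of drug-arm patients who crossed over to ablation will be censored at the time of the ablation". SAP 11 covers the primary endpoint and key secondary clinical outcomes, and only all-cause mortality is labelled key secondary.
- That CV hospitalization alone is affected in exactly the same way. SAP 9.2 words its rule for its own endpoint, so carry-over to 9.9 is an assumption. Nothing in 9.9 removes the crossover admission; without carry-over, nothing exempts the ablation arm's first ablation admission either, and that case was not simulated.

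**Conclusion.** The point holds for death or CV hospitalization and, assuming the SAP 9.2 counting rule carries over, for CV hospitalization. A crossover ablated during a site-designated CV admission, with no earlier counted one, has the exposure switch scored as the event. That patient can add no event-free ablated time, and date order decides which group is charged. This follows from the text and needs no simulation. All three coding methods share it, so the planned sensitivity analyses would not reveal it.

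The size rests on the assumptions above. With all crossovers admitted and no true effect, the HR is about 1.2–1.8 or 0.53–0.81 at 25–30% crossover and hazards of 0.08–0.25, about 1.15 or 0.86 at hazard 0.40, and about 1.04–1.27 or 0.77–0.96 at 10% crossover. It moves towards 1 as fewer crossovers are admitted or more have an earlier CV admission. A reader might infer that the trial's main results are compromised. They are not: the ITT analyses and the primary endpoint are unaffected. The change should be made because, for these endpoints, the analysis does not measure what it is meant to measure.

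**What to change.** Add to SAP 10, for death or CV hospitalization and for CV hospitalization:

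- In either arm, do not count as an event the admission at which the patient's first left atrial ablation is delivered, when the site gives ablation as the reason for admission. Keep the patient at risk and set the ablation variable to 1 on the ablation date.
- An admission for another CV reason, during which ablation is then performed, still counts. It is charged to the exposure state that applied at admission.

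Leave the ITT definitions in SAP 9.2 and 9.9 as they are, and make no change to SAP 11 on this account. The cost is a short insertion. Protocol 6.1 has sites report the reason for admission, and Protocol 9.2 has forms for the ablation procedure. The downside is that the on-treatment endpoint differs slightly from the ITT endpoint, which a footnote should state. The fix removes the overlap between event and exposure; it does not remove confounding from non-random crossover, which SAP 10 already acknowledges.

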5.4.2 Guidelines for Anticoagulation Therapy in Ablation Patients

Anticoagulation before, during, and after the ablative intervention will follow the guidelines of the AF Ablation Consensus Document [50]. Prior to the ablative intervention, patients with persistent and long-standing persistent AF should receive adequate anticoagulation (i.e. at least

one month of warfarin anticoagulation (INRs: 2-3)), or have a TEE excluding intra-atrial thrombus at the time of the intervention. During the ablative intervention, maintaining an ACT between 300 and 400 seconds is strongly recommended. Following the ablative intervention, patients will be started on IV heparin or subcutaneous injections of low molecular weight heparin beginning 4 to 6 hours after all sheaths are removed, and appropriate anticoagulation reinstated the evening of the intervention. Thereafter, low molecular weight heparin is to be maintained until anticoagulated appropriately or standard dose warfarin achieves a target INR of 2 to 3, unless the ablation was performed at a therapeutic INR in patients maintained on warfarin through the ablation. One month following the ablation, dabigatran, rivaroxiban or apixaban may be substituted for warfarin, following recently written guidelines. Three to six months after ablation, warfarin may be replaced by full dose aspirin in patients with a CHADs score ≤ 1 . This would include patients with hypertension without hypertrophy, or those < 65 years of age, providing 1) atrial size and function are normal and 2) there is no symptomatic or asymptomatic AF by standard or full-disclosure monitoring. In those patients with a CHADs score ≥ 2 , adequate anticoagulation is to be continued throughout the trial. Randomization of warfarin discontinuation is precluded by the low post-ablation stroke rates that would require at least 10,000 patients for detecting differences in stroke prevalence. Nevertheless, the characteristics, follow-up monitoring results, and long-term anticoagulation status of ablation patients will be compared to descriptively identify predictors of events and profiles of patients at high risk for warfarin discontinuation. The utility of trans-telephonic, auto-detection / full disclosure, and Holter monitoring, as a future aid in the decision to discontinue anticoagulation will also be critically examined.

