8.0 Statistical Considerations

8.1 Sample Size and Power Considerations

In initially planning the CABANA trial, several design factors and research objectives were considered in developing an appropriate sample size for the study. First, the number of patients was determined so there would be a sufficient number of endpoints to provide a high degree of confidence (power $\geq 90\%$) for testing the primary hypothesis. Second, important secondary endpoints were considered. Third, it was considered important for the overall sample to be large enough to permit a prudent examination of treatment effects in selected subgroups of patients where AF ablation might be particularly advantageous, or where the question of a treatment benefit from this invasive procedure is particularly relevant. Important pre-specified subgroups of interest in this study include those defined by age, gender, race, AF type (paroxysmal, persistent, or long-standing persistent), AF duration, heart failure class, presence/absence of underlying structural heart disease, presence/absence of hypertension, and ejection fraction. Finally, the sample size was determined to provide a reasonable level of confidence of detecting clinically important therapeutic effects even if current projections of event rates and treatment differences prove to be optimistic.

As described in Section 2.0, the study was originally designed with total mortality as the primary endpoint. However, in early 2013 a careful assessment of the progress of the trial was undertaken by the study leadership. Completely blinded to any treatment-specific outcome data, the two major issues addressed by the leadership group were (1) a lower than expected aggregated mortality rate, and (2) accrual of patients at a rate much slower than projected. Careful consideration of these issues led to a decision to (a) change the primary endpoint of the trial from total mortality to the key secondary endpoint consisting of the composite of death, disabling stroke, serious bleeding, or cardiac arrest, and (b) reduce the sample size to a number that was consistent with the new primary endpoint. The following paragraphs, which outlined the key considerations in determining the original sample size, are also relevant for the revised sample size.

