11.1 Site Selection and Monitoring

To qualify as an investigative site, each group must be committed to enrollment and randomization without bias or inclination toward early cross-over from drug to ablative therapy. Each site must also demonstrate the skill and expertise for participating in clinical trials as judged from their past trial performance. A Co-PI approach to the enrollment and treatment of patients will be required. A cardiac electrophysiologist skilled in the art of AF ablation will work closely with a non-interventional clinical cardiologist or internist. This will also help counter potential bias in favor of ablation. The focus of recruitment will be in Primary and Secondary Care clinics, Hospital ERs, and first referrals to ablation centers. Each site will be strongly encouraged to minimize the time between randomization and ablation to <2 weeks, by "holding" ablation slots.

As part of a concerted effort to follow the study in a detailed and orderly manner in accordance with established principles of Good Clinical Practice and applicable regulations, the Monitoring Plan is being revised with Executive Committee approval. A DCRI study monitor or their designee will no longer perform on-site visits to Active study sites regularly and throughout the study. Rather they will maintain frequent telephone and written communication, as well as perform on-site visits to a subset of sites to ensure data integrity.

The on-site monitoring visits will be made to assure that the Investigator obligations are fulfilled and all applicable regulations and guidelines are being followed. These visits will assure that the

facilities are still acceptable; the protocol and investigational plan are being followed, the IRB/EC has been notified of approved protocol changes as required, complete records are being maintained, appropriate and timely reports have been made to DCRI and/or their designee and the IRB/EC, study drug and study drug inventory are controlled and the Investigator is carrying out all agreed activities.

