7.2 Disposition of Subjects

The disposition of subjects (number randomized, number who received the randomly assigned treatment, number of treatment crossovers, number of patients who withdrew consent, and number lost to follow-up) will be summarized overall and by treatment arm. The summary of treatment crossovers will distinguish the patients randomized to the drug arm who subsequently underwent catheter ablation (crossed over to ablation) during the course of their follow-up and the patients randomized to the ablation arm who never received an ablation. The distribution of the length of follow-up for the overall study population and for each randomized arm will be characterized in terms of percentiles (median, 25th, and 75th percentiles). The number and percentage of patients who had at least 3 years of follow-up, and at least 5 years of follow-up will also be tabulated and reported. Among patients in the drug arm who crossed over to ablation, the distribution of length of follow-up prior to the crossover will be described in terms of percentiles. Also the distribution of follow-up among patients who withdrew consent (i.e., patients who withdrew prior to the protocol-specified 3 years of follow-up) will be summarized in terms of percentiles. Additionally, the number and percentage of patients who withdrew consent before 3 years, after 3 to <5 years, and after 5 years will be tabulated.

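### The main on-treatment method (SAP Section 10, Method 2) counts ablation-arm patients as ablated from randomization only if they are later ablated, which on its own tilts the hazard ratio for death towards ablation

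*SAP*

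**What the plan says.** SAP Section 10 supplements the intention-to-treat (ITT) comparison with a Cox model in which ablation is a time-dependent covariate. It covers the primary endpoint, all-cause mortality and most other clinical secondary endpoints. Time runs from randomization (SAP Section 8). The covariate is built in three ways:

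- Method 1: 0 for everyone, changing to 1 at ablation.
- Method 2: "In method 2, the ablation variable starts as 1 for all patients who were randomized to ablation and actually received ablation". Everyone else starts at 0 and changes to 1 at ablation, if it happens.
- Method 3: 1 from randomization for the whole ablation arm. Drug-arm patients change from 0 to 1 at ablation.

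On their ranking, "method 2 will be considered the main statistical method in handling cross-overs via a time-dependent variable in Cox model"; the other two are sensitivity analyses. The caution in Section 10 is about confounding: "factors that make a patient more likely to cross over may also make them more likely to have an event". SAP Section 11 makes all of this supplementary to ITT. Protocol 8.2.5 also uses a time-dependent covariate, spells out only the drug-arm crossover, and treats the analysis as exploratory.

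On reporting, SAP 7.2 counts ablation-arm patients who were never ablated. It adds: "Among patients in the drug arm who crossed over to ablation, the distribution of length of follow-up prior to the crossover will be described". It lists no matching item for the ablation arm's wait or for events before ablation. On the wait itself, Protocol 11.1 says: "Each site will be strongly encouraged to minimize the time between randomization and ablation to <2 weeks".

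**The concern.** Under Method 2 an ablation-arm patient's value on day 0 depends on something learned later. A patient who dies before the procedure falls among the others, stays at 0, and adds a death to the no-ablation group. A patient who survives the wait has that wait counted as ablated time, during which death was impossible by construction. Drug-arm crossovers are coded correctly, from the procedure date, so the two arms are handled differently.

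The printed caution does not cover this. It concerns who changes treatment, which affects all three methods; the coding problem belongs to Method 2 alone. Adjusting for baseline covariates cannot remove it, because it comes from using future information. At stake is how the estimate labelled main is read. The protocol allows for 25-30% drug-arm crossover, so readers may take that estimate as the crossover-corrected effect.

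**Working it through.** **Plan figures.** The plan gives no figure for this bias. As a check on the event-rate inputs I reproduced the stated power. A 12% three-year drug-arm rate, hazard ratio 0.70, 2,200 patients, uniform follow-up of 3-7 years and 2% loss give about 355 events. Power is Φ(0.3567 × √355 / 2 − 1.96) = Φ(1.40) = 0.919, against the stated 90%.

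**Inputs from the documents.** 2,204 patients randomized 1:1, so 1,102 per arm. Minimum follow-up is just under 2 years and median about 4 (SAP introduction), taken as uniform 2-6 years. Drug-arm crossover is 25-30% (Protocol 8.1), taken as 27.5% by 5 years.

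**Assumptions.** No true effect and no confounding, so the coding acts alone. Waits are exponential. 5% of the ablation arm is never ablated. Three-year mortality is 6%, half the 12% planning rate for the composite, since Protocol 8.1 reports "a lower than expected aggregated mortality rate".

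**Hazard shapes.** Cumulative hazard is H(t) = H₃(t/3)^k, with H₃ = −ln(0.94) = 0.0619.

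- Constant: k = 1.
- Rising: Protocol 8.1 projects 12% mortality at 3 years and cites 21.3% and 23.8% at 5 years in AFFIRM, about 22.5%. Then k = ln[ln(0.775)/ln(0.88)] / ln(5/3) = 0.690/0.511 = 1.35.
- Falling: k = 0.8, an assumption with no support in the documents, shown for range.

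**Step 1: deaths moved.** Expected ablation-arm deaths during a wait of mean w years are m = 1,102 × 0.95 × H₃ × (w/3)^k × Γ(1+k). For k = 1 and 14 days (w = 0.0383), m = 1,046.9 × 0.0619 × 0.01278 = 0.83.

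**Step 2: effect on the hazard ratio.** Let D₁ and D₀ be the deaths with and without ablation before any are moved. Then HR ≈ (1 − m/D₁)/(1 + m/D₀). For k = 1 the yearly hazard is λ = 0.0619/3 = 0.0206. Total deaths are 2,204 × [1 − (e^(−2λ) − e^(−6λ))/(4λ)] = 174. Simulated person-years split about 4,530 to 3,900, so D₁ = 93.4 and D₀ = 80.4. At 14 days, HR = (1 − 0.0089)/(1 + 0.0103) = 0.98. The simulated D₁ and D₀ are 106.5 and 88.0 for the rising hazard, and 86.6 and 77.0 for the falling one.

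| Mean wait (days) | Constant: m, HR | Rising: m, HR | Falling: m, HR |
|---|---|---|---|
| 14 | 0.8, 0.98 | 0.2, 1.00 | 1.8, 0.96 |
| 30 | 1.8, 0.96 | 0.6, 0.99 | 3.4, 0.92 |
| 60 | 3.6, 0.92 | 1.5, 0.97 | 5.9, 0.87 |
| 90 | 5.3, 0.88 | 2.7, 0.95 | 8.2, 0.82 |

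Cox fits to 2 million simulated patients per arm agree to within 0.01. Methods 1 and 3 gave 0.996-1.007 in every cell. The mortality level hardly matters, because m and the death counts scale together: at 9% (about 259 deaths, constant hazard) Method 2 gives 0.98, 0.96, 0.92 and 0.88.

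**Step 3: composites.** Only events that prevent a later ablation cause the shift. With a 12% three-year rate, constant hazard and 60% of pre-procedure events preventing ablation, Method 2 gives 0.99, 0.98, 0.95 and 0.93 at the four waits. At 30% it gives 1.00, 0.99, 0.97 and 0.96. At 0% there is no shift under the null, and with a true hazard ratio of 0.70 Method 2 reads 0.70-0.74 (mean waits of 0.5 to 6 months), level with or slightly closer to 1 than Method 1.

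**Step 4: adding confounding.** Suppose 30% of patients have twice the hazard and cross over at two or three times the rate. Method 1 then reads 1.03 or 1.06. Method 2, for death with a constant hazard, reads 1.01 or 1.04 at 14 days and 0.95 or 0.97 at 60 days.

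**The case against.** The strongest reply has four parts.

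First, the shift may be very small. The one stated goal for the wait is under 2 weeks, and the protocol's own mortality figures imply a rising hazard; together these put the hazard ratio at about 1.00. The longer rows also sit poorly with the three-month treatment initiation period (Protocol 4.4) and with post-ablation imaging timed between 90 days after ablation and the 6-month visit (Protocol 4.4.2). An exponential wait with a 90-day mean would put e^(−91.3/90) = 36% of procedures beyond 3 months. This stands as a limit on size. It does not settle the matter: the goal is only encouraged, Protocol 5.4.2 allows a month of anticoagulation before ablation (imaging is the alternative) in persistent AF, and SAP Section 11 plans per-protocol windows of 3, 6 and 12 months. The hazard in the first weeks is not documented.

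Second, the analysis is supplementary and carries no alpha, and Methods 1 and 3 will be run beside it, so a gap would be visible. This stands and limits the severity. Without the wait and the pre-ablation events, though, readers could not explain a gap.

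Third, promoting Method 1 has a trap of its own. Times are in whole days (SAP Section 8), and the usual (start, stop] coding would count a procedure-day event as no-ablation, which also favours ablation. If 0.5% of patients had such an event (assumed), that is 0.005 × 1,102 = 5.5 events, more than the 0.8 deaths moved at 14 days under a constant hazard. This stands, and the fix must deal with it.

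Fourth, recurrent AF is outside the point. SAP 9.8 restricts that analysis to patients who received their assigned treatment and survived the blanking period, and starts the clock at its end. This also stands.

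A reader might infer that the on-treatment result must overstate ablation. The documents do not support that: Section 10 warns of crossover confounding, and Step 4 shows it can outweigh the coding shift.

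**Conclusion.** The coding flaw is real and follows from the SAP's wording. Taken alone, Method 2 shifts the on-treatment hazard ratio towards ablation for death, and less so for composites containing death. For endpoints made up mostly of non-fatal events the shift may be nil.

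The size is a range, not an estimate. With no true effect, the hazard ratio for death at a mean wait of 14 days is about 0.98 (constant hazard), 1.00 (rising) or 0.96 (falling). At an assumed 90 days it is about 0.88, 0.95 or 0.82. These figures rest on exponential waits, the assumed crossover and never-ablated shares, and the absence of confounding.

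No net direction is claimed. It would also be wrong to infer that the trial's main conclusion is at risk, since ITT does not use this covariate. Severity is minor to should-fix: the analysis is supplementary, but the avoidable flaw sits in the version labelled main.

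**What to change.** In SAP Section 10:

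- Make Method 1 (0 until ablation, then 1, in both arms) the main on-treatment method.
- Add a procedure-day rule: events on that day at or after the start of ablation count as ablation events. For example, switch the covariate at the start of the procedure day and count as no-ablation only events documented as preceding the procedure.
- Keep Method 3 as a sensitivity analysis, noting that it treats never-ablated ablation-arm patients as ablated.
- Demote Method 2 to a sensitivity analysis, labelled as conditioning on future ablation.

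In SAP 7.2, report for the ablation arm the randomization-to-ablation interval (median, 25th and 75th percentiles) and the number of deaths and primary-endpoint events before ablation.

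The cost is a few sentences. All three methods are already specified, and Protocol 8.2.5 needs no change. Where timing on the procedure day is unclear, source records may have to be checked. The downside is that the on-treatment estimate may look slightly less favourable to ablation, and if sicker drug-arm patients cross over, Method 1 can read above 1 with no true effect.
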